Hydroxychloroquine (HCQ, Plaquenil) is an anti-inflammatory agent used to treat systemic lupus erythematosus, rheumatoid arthritis, Sjorgen's Syndrome and porphyria cutanea tardus. It has been noted that patients with rheumatoid arthritis and psoriasis taking HCQ exhibited a decreased risk for developing diabetes (Wasko MC, et al. JAMA 2007; 298:187-193; Solomon DH, et al. JAMA 2011; 305:2525-2531). These findings are consistent with isolated case reports of hypoglycemia in type 2 diabetic patients on the drug (Shojania K, et al. J. Rheumatol 1999; 26:195-196), its inclusion as a possible 3rd line agent in a review of treating type 2 diabetes (Llarde A, Tuck M. Drugs Aging 1994; 4:470-491), and its effect on decreasing glycemia in patients with type 2 diabetes (Gerstein HC, et al. Diabetes Res Clin Pract 2002;55:209-219; Rakedal LR, et al. Arthritis Rheum 2010;62:3569-3573; Quatraro A, et al. Ann Intern Med 1990;112:678-681). In a more recent study, HCQ (6.5 mg/kg) given to 13 obese non-diabetic subjects for 12 weeks significantly increased insulin sensitivity (as measured by the Matsuda Insulin Sensitivity Index) at 6 weeks with a return to baseline at 12 weeks (Mercer E, et al. Arthritis Res Ther 2012).

This pilot study will compare the efficacy of HCQ and pioglitazone (PIO) in patients who have failed maximum doses of metformin plus an SU. Ultimately, if HCQ proves to be as effective as PIO, another modality of treatment will be available with a drug that has fewer side effects. Even if HCQ is not as effective but does significantly lower HbA_{1c} levels, it may represent another drug for patients in whom PIO may be contraindicated. We also plan to monitor highly sensitive C-reactive protein (hsCRP) as a marker of inflammation, and since the anti-inflammatory properties of HCQ are well established, we anticipate that hsCRP levels will decrease. If insulin sensitivity does not improve or worsens with HCQ, we would conclude that inflammation does not contribute insulin resistance. Should both insulin resistance and

inflammation be reduced, further research would be needed to determine if the two change independently of each other or if either one could contribute to the other.

Primary Outcome: To collect preliminary data as to whether HCQ may ultimately be non-inferior to PIO in lowering HbA_{1c} levels in type 2 diabetic patients failing maximum doses of metformin and SU.

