- Known history of Class III or IV heart failure, cardiac arrhythmias, severe peripheral edema, advanced osteoporosis, documented bladder malignancies, or other intolerance to PIO
- Known history of collagen vascular disorders, glucose-6-phosphate dehydrogenase deficiency, hematologic disorders, psoriasis, or any known intolerance to HCQ

- Known history of pre-proliferative or proliferative retinopathy, or any clinically significant retinal abnormalities noted on the patient's most recent (i.e., within 1 year) ophthalmologic exam; subjects who have not received their routine annual ophthalmologic surveillance for diabetic retinopathy within the past year must have their annual surveillance performed before screening
- An estimated GFR (by the Modification of Diet in Renal Disease (MDRD) formula) < 45 mL/min, or a history of nephrotic syndrome (defined as a spot urine protein-creatinine ratio of > 3500 mg per g urine creatinine)
- Subjects with active hemoglobin abnormalities that render the HbA_{1c} measurement unreliable
- History of any clinically significant hepatic, cardiovascular, infectious, dermatologic, psychiatric, or other major systemic disease that, in the opinion of the investigator, may make the use of PIO or HCQ unsafe, or otherwise make the interpretation of the data difficult.
- Female subjects of childbearing potential who are sexually active and not using a reliable form of contraception or do not agree to use a reliable form of contraception. Reliable forms of contraception include systemic contraceptives (oral, implant or injection), diaphragm with spermicide, cervical cap, IUD, or condoms with spermicide.
- Current pregnancy or lactation.
- Subjects who will likely require or initiate therapy with drugs that may interfere with glucose metabolism during the course of the study (e.g., glucocorticoids).
- Subjects who are in another investigational study or have received another investigational medication within 30 days of study entry
- Subjects who are unable or unwilling to give informed consent, comply with all components of the study protocol, attend all scheduled follow-up visits, or present other barriers that would make the implementation of the protocol unusually difficult.

Schedule of Procedures: This study will be approximately 4 months in duration. Subjects will be assessed at baseline, 2 and 4 months. All visits will include an assessment of:

- Fasting plasma glucose (FPG)
- HbA_{1c}

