Screening Visit (Week 0): Consent, screening, review of inclusion and exclusion criteria, and all required subject assessments for the study will take place at the CDU CTRC. A signed authorization for the release of medical records from MLK or SCFHC for the purposes of this study will be needed from all consented subjects to permit the investigators to review the relevant results when they become available. If all entry criteria are met, blood will be taken for the following laboratory tests: CBC, electrolytes, BUN, creatinine, FPG, HbA_{1c}, AST, ALT, fasting insulin, and hsCRP; urine will be collected for a urine pregnancy test (for women of childbearing potential). For subjects from MLK, all blood and urine samples with the exception of fasting insulin and hsCRP will be drawn by the MLK outpatient phlebotomists as per the diabetes clinic's routine treatment protocols, and the investigators will retrieve those results for review when they become available; fasting insulin and hsCRP blood samples will be obtained separately by phlebotomists at the CTRC. The above laboratory tests with the exception of fasting insulin and hsCRP are not required if they have already been performed by the laboratory within the previous 4 weeks and the results are accessible to the study team. For subjects from SCFHC, any of the above laboratory test results performed within the previous 4 weeks will be requested by the investigators, and any that were not performed within the previous 4 weeks will be drawn by the CTRC (including the fasting insulin and hsCRP).

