as with Week 0, all samples except fasting insulin and hsCRP will be obtained by the MLK phlebotomists and results will be reviewed when available; urine will be collected and processed by the MLK laboratory for a urine pregnancy test for women of childbearing potential at each follow-up visit; fasting insulin and hsCRP samples will be obtained separately at the CTRC. For subjects from SCFHC, all samples will be obtained at the CTRC (since the distance from SCFHC to CDU makes obtaining routine lab tests at SCFHC unrealistic when visits must take place at the CTRC). Based on current clinical evidence, diabetic patients are not required to perform self-glucose monitoring in the absence of insulin use, although subjects may perform self-glucose monitoring on their own if desired. Any hypoglycemic symptoms or any other adverse experiences will be reviewed and an attempt will be made to explain their occurrence. The subject's concurrent medications will be reviewed to ensure that dosages and compliance have not changed; any changes will be logged and subjects will be appropriately counseled. The entire study will last approximately 4 months.

Visit #	1	2	3
Week	0	8	16
Consent, inclusion / exclusion criteria	X		
Review of history / physical findings	X	X	X
CBC, Chemistry, FPG, HbA _{1c} , Urine pregnancy test ^a (obtained at MLK, SCFHC or CTRC)	X	X	X
Vitals, Weight, Height	X	X	X
Fasting insulin, calculation of HOMA-IR and QUICKI, hsCRP (obtained at CTRC, banked)	X	X	X
Randomization (if all criteria met)	X		
Dispense study medication supply	X	X	
Collect unused study medication supply; pill counts		X	X
Review of hypoglycemia	X	X	X
Review of adverse events		X	X
Reinforce nutrition / lifestyle	X	X	X
Review concurrent medications	X	X	X

^a For women of childbearing potential.

Assessment Measures (performed at CTRC):

- Vital signs, height and weight will be obtained at each visit, along with a brief review of the patient's history and physical findings at week 0 to look for exclusion criteria.
- Compliance with the subject's usual nutritional and lifestyle activities will be reviewed and reinforced.
- Changes in concurrent medications will be assessed at each encounter. Every effort will be made to avoid changes in concurrent medications that may influence carbohydrate or lipid metabolism (unless down-titration of SU is required).

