- Compliance with the study medication will be verified with pill counts at each follow-up visit. The need for consistent use of the study medication will be reinforced if suboptimal compliance is noted.
- Adverse events and any clinically meaningful changes in physical findings will be noted. The probability of any causal relationship between the adverse event or physical finding

and the study intervention will be judged by the investigator and if necessary, reported to the IRB.

- Hypoglycemic episodes, as defined by the presence of appropriate symptoms that are alleviated by the ingestion of carbohydrates or associated with a confirmed FPG level < 60 mg/dL, will be assessed. If necessary, subjects will be instructed on how to manage hypoglycemic reactions if they have not previously received such instructions. The frequency and timing of episodes will be noted. Possible precipitants of hypoglycemia will be reviewed and corrective measures will be advised if correctable precipitants are identified. If necessary, the subject's SU dosage may be down-titrated to alleviate any recurrent hypoglycemic episodes.

Withdrawals: Subjects may either voluntarily withdraw from the study or be withdrawn by the investigators. A subject who withdraws from the study for any reason will continue to be followed for their diabetes in their respective Diabetes Clinic after their study participation is terminated. Reasons for study withdrawal by the research team include, but are not limited to, excessive non-compliance with the study medication, repeated failure to attend scheduled visits, use of any other medications known to affect glucose or lipid control, adverse effects (including confirmed FPG ≥ 300 mg/dL or clinically significant hypoglycemia not relieved by nutritional modifications or downward titration of the SU) or any other clinical situation which, in the opinion of the investigators, may jeopardize the subject's safety.

Methodologies:

Anthropometric Measurements: Standard procedures will be followed for the measurement of vital signs, weight, height, and calculated BMI.

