Laboratory Measurements: All laboratory analyses except fasting insulin and hsCRP will be obtained by the respective clinic phlebotomists specified above, and conducted by the respective clinical laboratories specified above, or the CTRC. Samples for insulin and hsCRP levels will be obtained at the CTRC, banked, and will be measured in the future by the CTRC Core Lab using commercially available RIA and/or ELISA kits: Millipore HI-14K Human Insulin RIA (Millipore, Billerica, MA); MP Biomedicals 07BC-1119 ultrasensitive CRP ELISA (MP Biochemicals, Orangeburg, NY); samples for insulin and hsCRP will remain frozen until assay reagents are available for batched runs once all samples have been collected.

Statistical Analyses:

All data will be collected onto Excel spreadsheets. Non-normal data will be log-transformed, as appropriate.

Intended Primary Endpoint: *The between-group change in the HbA_{1c} level from baseline to 4 months.*

Intended Secondary Endpoints:

A) The between-group difference in the change by 4 months of: i) % of subjects achieving HbA_{1c} $< 7.5\%$, ii) FPG, iii) weight and BMI, iv) HOMA-IR and QUICKI, and v) hsCRP and leukocyte counts;

B) For each group, the within-group change by 4 months in HbA_{1c}, FPG, weight and BMI, HOMA-IR and QUICKI, hsCRP, and leukocyte counts;

C) The between-group difference in the incidence of i) all hypoglycemic events, ii) severe hypoglycemic events, and iii) all adverse events excluding hypoglycemia.

Analysis: Changes in all continuous outcome measures will be compared between groups using 2-way repeated measures ANOVA. A chi-square analysis will be used to compare the percent of subjects achieving HbA_{1c} $< 7.5\%$ between groups. Changes within groups between baseline and

4-months will be made with one-way ANOVA. We will plan to eventually conduct both an intent-to-treat (ITT) analysis (missing data imputed using last-observation carried forward) as well as a secondary analysis of only those completed subjects with mean medication compliance $\geq 90\%$.

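### LOCF is the only missing-data rule, the target effect is not fully specified and the use of HbA1c after withdrawal is not settled, so the week-16 HCQ-PIO difference can be biased in either direction

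*Combined protocol and SAP*

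**What the plan says.** Under Statistical Analyses, the Analysis paragraph gives one rule for missing data: "We will plan to eventually conduct both an intent-to-treat (ITT) analysis (missing data imputed using last-observation carried forward". The only other planned analysis is restricted to completers with mean compliance of at least 90%. Continuous outcomes are compared by 2-way repeated measures ANOVA, and the proportion below 7.5% by chi-square. The intended primary endpoint is the between-group difference in HbA1c change over 4 months.

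The Schedule of Procedures sets the measurement times: "Subjects will be assessed at baseline, 2 and 4 months".

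The Withdrawals section ties several exits to treatment or outcome. "Reasons for study withdrawal by the research team include, but are not limited to, excessive non-compliance with the study medication"; the list goes on to other drugs affecting glucose, and to adverse effects that include confirmed FPG of 300 mg/dL or more. It adds that a withdrawn subject "will continue to be followed for their diabetes in their respective Diabetes Clinic after their study participation is terminated".

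Under Screening Visit (Week 0), every consented subject must sign a records release: "A signed authorization for the release of medical records from MLK or SCFHC for the purposes of this study will be needed". No section says whether HbA1c found in those records after withdrawal enters the analysis.

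**The concern.** With only two post-baseline visits, LOCF has just two values to carry. A baseline value says the drug did nothing. A week-8 value says its effect froze halfway through the study. Both are then treated as observed week-16 measurements. The completer analysis drops the same patients and selects on behaviour after allocation, so agreement between the two analyses would not show that LOCF is harmless.

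Whether a carried value is too good or too bad depends on what is being estimated. For the effect had everyone stayed on drug, a patient who leaves while still improving is under-credited. For the effect regardless of stopping, a patient who leaves and loses the benefit is over-credited. The ITT label leans towards the second, but a value measured before withdrawal does not estimate it.

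The time course matters too. The only HCQ time course in the Background comes from 13 obese non-diabetic subjects, in whom the drug "significantly increased insulin sensitivity (as measured by the Matsuda Insulin Sensitivity Index) at 6 weeks with a return to baseline at 12 weeks". That is insulin sensitivity, not HbA1c. If HbA1c behaved the same way, a carried week-8 value would preserve an effect that had faded.

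The pilot is meant to show whether efficacy may be similar and whether full funding is worth seeking. LOCF is also the rule for the eventual full analysis, where a larger sample would reduce imprecision but not this bias.

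**Working it through.** The plan has no figure of its own to reproduce here: it states no drop-out rate, SD, HCQ effect on HbA1c or week-8 effect.

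**From the documents.** Visits at weeks 0, 8 and 16; a fall of about 2.0 points at 4 months on a TZD, from a baseline of 9.3-9.5% (Background); up to 60 subjects (Sample Size Calculations), taken here as 30 per arm.

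**Assumed.** PIO change -1.2 at week 8. HCQ change -0.8 at week 8 and -1.2 at week 16. Drop-out d = 20% per arm. Share f of drop-outs leaving before week 8 from 0 to 0.5. Leavers are back at baseline by week 16.

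**Formulas**, per arm, with C8 and C16 the on-drug changes:
- LOCF mean = (1-d) x C16 + d x (1-f) x C8
- On-drug mean = C16
- Mean regardless of stopping = (1-d) x C16
- Gap = HCQ minus PIO; a positive gap favours PIO

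**Case A.**
- f = 0: PIO 0.8 x (-2.0) + 0.2 x (-1.2) = -1.84; HCQ 0.8 x (-1.2) + 0.2 x (-0.8) = -1.12; gap 0.72.
- f = 0.5: PIO -1.72; HCQ -1.04; gap 0.68.
- On drug: -1.2 + 2.0 = 0.80. Regardless: -0.96 + 1.60 = 0.64.

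**Other cases**, same formulas. B: HCQ wanes (-0.8, then -0.4). C: equal drugs (-1.2, then -2.0), drop-out 30% PIO and 10% HCQ. D: equal drugs, 20% per arm, all PIO losses before week 8 and all HCQ losses after it.

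| Case | LOCF gap | On drug | Regardless | Error v. on drug | Error v. regardless |
|---|---|---|---|---|---|
| A | 0.72 to 0.68 | 0.80 | 0.64 | -0.08 to -0.12 | +0.08 to +0.04 |
| B | 1.36 to 1.32 | 1.60 | 1.28 | -0.24 to -0.28 | +0.08 to +0.04 |
| C | -0.16 to -0.28 | 0 | -0.40 | -0.16 to -0.28 | +0.24 to +0.12 |
| D | -0.24 | 0 | 0 | -0.24 | -0.24 |

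In A to C the sign of the error changes with the target.

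**Would a likelihood model of on-drug data be better?** If drop-out depends only on observed values, it estimates the on-drug gap. Against the effect regardless of stopping it then gives 0.80 for 0.64 (error 0.16), 1.60 for 1.28 (0.32) and 0 for -0.40 (0.40) in cases A to C. LOCF is closer in all three.

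**Drop-out linked to HbA1c** (assumed SD 1.0-1.5, correlation between visits 0.5-0.7; on-drug target):
- Patients with no fall at week 8 leave. LOCF gives 0.78-0.84 against 0.80 (A) and 1.34-1.47 against 1.60 (B). This drop-out meets the likelihood model's assumption, so the model recovers 0.80 and 1.60.
- Patients whose unseen week-16 value shows no fall leave (A). LOCF gives 0.72-0.79 and the model about 0.56-0.70, against 0.80. Adding +1.0 to the imputed HCQ values brings the model to 0.77-0.82.

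**Responders** (assumed baseline 9.4, SD 1.0 at each visit, 20% per arm lost at random after week 8; A). Week 16: 54.0% - 24.2% = 29.8 points. Week 8: 24.2% - 13.6% = 10.6 points. LOCF: 0.8 x 29.8 + 0.2 x 10.6 = 26 points, against a true 30.

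**Precision.** 95% half-width = t(0.975, 58) x SD x sqrt(2/30) = 2.00 x 0.258 x SD, which is 0.52 (SD 1.0) to 0.78 (SD 1.5).

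**Wider grid** (HCQ -1.0 to -2.0; week-8 effect 50-90% of week 16; drop-out 10-30% per arm; none to all drop-outs with a week-8 value; leavers' week-16 change 0 to -2.0). The LOCF error runs from -0.50 to +0.40 against the on-drug gap. Against the gap regardless of stopping it runs from -0.40 to +0.45 if leavers end at the same change in both arms, and from -0.60 to +0.87 if that may differ by arm.

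**The case against.** The strongest objection is that replacing LOCF outright could make matters worse. That stands. Without retrieved values, a likelihood model is further than LOCF from the effect that the ITT label suggests in cases A to C, and it also loses when unseen non-response drives drop-out. The method can be chosen only after the target is fixed.

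It is also fair that this is a pilot, that the ITT analysis is something to be done eventually, and that no margin or go/no-go threshold is stated, so no written decision rule would flip. Nearly all the inputs above are assumed, and nothing in the documents suggests the timing pattern in case D. These points limit the severity; they do not supply the missing rules. An interval shows imprecision, but it does not show this bias.

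A reader might infer three stronger things that the documents do not support:
- That no target effect is stated at all. The plan names the 4-month between-group change and labels the analysis ITT; the target is incompletely specified, not absent.
- That LOCF necessarily favours HCQ or pulls the arms together. It shrinks the gap in some cases, enlarges it in others and creates one in case D.
- That HCQ's HbA1c effect is known to wane. The cited finding concerns insulin sensitivity in non-diabetic subjects.

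**Conclusion.** The point holds, with moderate consequence. LOCF is the only stated missing-data rule, the completer analysis does not test it, and the plan leaves open both the exact target effect and the use of HbA1c after withdrawal. The resulting bias can take either sign.

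Its size cannot be fixed from the documents. In the worked cases it is at most 0.28 points, below the pilot's half-width of 0.52 to 0.78. Only the widest set of assumptions, with leavers ending at different levels in the two arms, reaches errors of that order. The omission is certain; the figures are illustrations that rest on assumed drop-out, time courses and SDs. They do not show that the pilot's result would be wrong, only that a reader could not tell how far, or in which direction, drop-out had moved it.

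**What to change.** Amend the Analysis paragraph in this order, and say that it applies to the pilot data as well as to the eventual full analysis.

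1. State the target effect for week-16 HbA1c: regardless of stopping the study drug, or as if all had stayed on it.
2. Match the method to the target.
   - *Regardless of stopping* (which the ITT label suggests): use clinic-record HbA1c near week 16 for withdrawn patients, where consent has not been withdrawn and the release covers it. A 4-week window is one option, since at screening the plan already says for SCFHC that "any of the above laboratory test results performed within the previous 4 weeks will be requested by the investigators". Report how many values were retrieved. Multiply impute the rest from retrieved drop-outs or, if these are too few, under a stated assumption such as return towards baseline. Do not rely on a likelihood model of on-drug data alone.
   - *On drug*: replace LOCF with a likelihood-based repeated-measures model (arm by visit, baseline HbA1c) or multiple imputation.
3. Add a sensitivity analysis that shifts imputed week-16 values in each arm separately and in both directions, for example from -1.0 to +1.0 points.
4. Classify HbA1c <7.5% from the multiply imputed week-16 values, not from carried week-8 values.

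The cost is a short paragraph, an imputation run and record retrieval for the drop-outs among at most 60 patients. Retrieval will not succeed for everyone: clinic values may not fall near week 16, and for study visits the plan notes that "the distance from SCFHC to CDU makes obtaining routine lab tests at SCFHC unrealistic when visits must take place at the CTRC". Intervals will be somewhat wider, and the result will rest on missing-data assumptions, but stated ones. The clinical withdrawal criteria are unchanged.

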Secondary Outcomes: To collect preliminary data to eventually compare a) the percentage of patients who achieve HbA_{1c} <7.5% after receiving either HCQ or PIO for 4 months; b) the effect of PIO vs. HCQ in lowering fasting plasma glucose (FPG) and weight; and c) the effects of HCQ vs. PIO on inflammation and insulin resistance.

Research Design: A 4-month, randomized, prospective, open-label comparison trial

Subjects: Type 2 diabetic patients inadequately controlled on maximally tolerated doses of metformin plus a SU.

Recruitment: Subjects will be recruited from the Diabetes Programs at MLK and South Central Family Health Center (SCFHC). These centers serve the same large population of low-socioeconomic status and low-educational level ethnic minority patients living in the south and south-central region of Los Angeles. The diabetes clinic at MLK is staffed by the faculty of the Endocrinology Division of Charles R. Drew University of Medicine and Science, and the diabetes care providers at the SCFHC clinic were trained on the same treatment protocols by the study co-investigator. This study protocol will be reviewed by the Institutional Review Board of Charles R. Drew University prior to study initiation, and an IND application will be submitted to the FDA.

Inclusion Criteria:

- Male or female, age 18-75, inclusive
- Known type 2 diabetes (diagnosed according to 1997 ADA diagnostic criteria) receiving diabetes treatment at MLK or SCFHC
- At least 3 months of treatment with maximum tolerated doses of metformin *and* a SU, *and* inadequate glycemic control (HbA_{1c} ≥ 7.5% and < 11.0%)
- Body mass index (BMI) < 45 kg/m²
- Able to comply with all scheduled visits and requirements of the protocol

Exclusion Criteria:

- Any contraindications to the use of metformin or a SU
- Extreme hyperglycemia (FPG ≥ 300 mg/dL), symptoms of polyuria or polydipsia, or HbA_{1c} ≥ 11.0%
- Current use of insulin; history or clinical suspicion of type 1 diabetes mellitus
- Symptomatic hypoglycemia occurring at an average frequency > once per day
- Highly erratic dietary schedules, extremely food insecure households, or homelessness that may adversely affect good glycemic control, as judged by the investigators
- Occupations that involve regular operation of motor vehicles or other heavy machinery that may pose a hazard in the event of unanticipated blurred vision

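### Limiting the compliance analysis to completers drops compliant subjects withdrawn for FPG ≥ 300 mg/dL, and this can understate a true HCQ–PIO difference

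*Combined protocol and SAP*

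**What the plan says.** The Analysis paragraph under Statistical Analyses plans two analyses. One is ITT, with "missing data imputed using last-observation carried forward". The other is "a secondary analysis of only those completed subjects with mean medication compliance" of at least 90%. The plan does not define *completed*.

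The Withdrawals section gives reasons for which the research team may withdraw a subject. Among them are "adverse effects (including confirmed FPG ≥ 300 mg/dL or clinically significant hypoglycemia not relieved by nutritional modifications or downward titration of the SU". A subject who withdraws for any reason "will continue to be followed for their diabetes in their respective Diabetes Clinic after their study participation is terminated".

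The primary endpoint is the between-group change in the HbA1c "level from baseline to 4 months". FPG and the percentage reaching HbA1c < 7.5% are secondary endpoints. The Primary Outcome statement asks "whether HCQ may ultimately be non-inferior to PIO in lowering" HbA1c.

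**The concern.** The 90% compliance condition has a clear purpose: it selects subjects who took the drug. The completion condition does something else. FPG is itself a study endpoint and is closely tied to HbA1c. A subject who took every tablet and was withdrawn because fasting glucose reached 300 mg/dL has failed on the assigned drug, yet leaves the analysis as if he or she were an ordinary dropout. Classing the event as an adverse effect hides that it is also an efficacy failure.

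The trial looks toward a future claim that HCQ is not inferior to PIO. In that setting, removing failures matters most when they fall more often in the weaker arm, since the estimated difference then shrinks toward zero. This differs from the question of carrying observations forward in the ITT analysis: here the subjects are deleted, not imputed.

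**Working it through.** **1. The exclusion, from the text.** Compliant subject → confirmed FPG ≥ 300 mg/dL → withdrawn (Withdrawals) → participation terminated (same section) → not completed → outside the compliance set (Analysis). No other section brings the subject back or counts the subject as a failure in that set.

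**2. When it can happen.** FPG is scheduled at weeks 0, 8 and 16 only (Schedule of Procedures; visit table), and self-monitoring is not required (Follow-Up Visits). A subject first found at or above 300 mg/dL at week 16 already has the final HbA1c and would most naturally count as completed. The loss therefore concerns mainly failures found at week 8 or at an unscheduled visit.

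**3. Inputs for size.** The plan has no figure to reproduce: it states no withdrawal rate, SD, margin or power.
- From the documents: a reduction of about 2.0 HbA1c points with TZDs (Background); at most 60 subjects (Sample Size Calculations), so about 30 per arm.
- Assumed: the HCQ mean change, the number withdrawn per arm, and a mean change among those withdrawn of 0 to +1.0.

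**4. Effect on the mean difference.** For an arm with mean change μ over all its subjects, share withdrawn w, and mean change m among those withdrawn:

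completer mean = (μ − w·m) / (1 − w)

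Example: HCQ μ = −1.5, 3 of 30 withdrawn, m = 0, gives −1.5/0.9 = −1.667. PIO μ = −2.0, 1 of 30 withdrawn, m = 0, gives −2.0/0.9667 = −2.069. The completer difference is 0.40, against a true 0.50.

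| Withdrawn HCQ / PIO | True difference 0.50: m = 0 to m = +1.0 | True difference 1.00: m = 0 to m = +1.0 |
|---|---|---|
| 3 / 1 | 0.40 to 0.33 | 0.96 to 0.88 |
| 5 / 1 | 0.27 to 0.10 | 0.87 to 0.70 |
| 3 / 3 | 0.56 (either m) | 1.11 (either m) |

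With equal counts the gap does not shrink, although each arm's own mean still looks better than it is.

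**5. Letting the withdrawals follow from the outcome.** This simulation used 1,000,000 subjects per arm, Normal changes, PIO mean −2.0, SD 1.0 to 2.0, and withdrawal when the HbA1c change exceeds +0.5 or +1.0. That cut stands in for FPG ≥ 300 mg/dL and is an assumption.

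| True difference | HCQ withdrawn | PIO withdrawn | Completers only | Failures set to baseline (no change) |
|---|---|---|---|---|
| 0 | 0.1–10.5% | 0.1–10.6% | 0.00 | 0.00 |
| 0.50 | 0.6–15.9% | 0.1–10.6% | 0.33–0.49 | 0.41–0.49 |
| 1.00 | 2.3–22.7% | 0.1–10.6% | 0.63–0.95 | 0.78–0.97 |

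The simulation removes every failure, including any that would first appear at week 16, so it leans toward the larger effect. The last column shows the softest form of carrying forward, which applies to a subject with no HbA1c after baseline.

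**6. Effect on the responder rate.** Suppose 15 of 30 compliant subjects in an arm reach HbA1c < 7.5%: 15/30 = 50.0%. Dropping 3 failures gives 15/27 = 55.6%. Dropping 6, a high figure given step 2, gives 15/24 = 62.5%.

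**The case against.** The strongest reply is that little rests on this set. The plan calls it secondary, both analyses are intended for eventual use, no margin is stated, and Sample Size Calculations concedes that the pilot will miss its intended power. The ITT analysis keeps the withdrawn subjects. Because FPG ≥ 300 mg/dL is classed as an adverse effect, it should also appear in the between-group comparison of adverse events and in the quarterly safety review. All of this stands and limits the weight of the point. None of it corrects the compliance set. The ITT analysis is not a full safeguard either: a subject withdrawn before the week 8 HbA1c carries baseline forward as no change, which also softens a failure.

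A reader might infer more than the documents support:
- *The weaker arm is bound to look better relative to the other.* The withdrawal reasons are grounds on which investigators may act, not an automatic rule, and the between-arm effect needs unequal withdrawals. Step 5 shows none when the drugs are equally effective, and some shrinkages are trivial (0.50 to 0.49).
- *A small rise in glucose is enough, because entry is barred only by* "Extreme hyperglycemia (FPG ≥ 300 mg/dL" *and above.* That holds only for subjects who enter just under the limit. The documents give no FPG distribution. Entry also excludes HbA1c ≥ 11.0% and polyuria or polydipsia, and the sites' earlier third-drug experience had baseline HbA1c of 9.3–9.5%.
- *The compliance set is the plan's test of whether the ITT result can be trusted.* The plan gives it no such role.

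**Conclusion.** The point holds in limited form. As written, the compliance analysis omits compliant subjects withdrawn for confirmed FPG ≥ 300 mg/dL before week 16, and it does so because of their outcome. If the less effective arm loses more of them, the analysis can understate the HCQ–PIO difference. With equally effective drugs no between-arm bias is expected.

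The size is unknown. The illustrations run from a negligible change to most of a 0.50-point difference (0.10 left with 5 versus 1 withdrawals), and every one rests on assumed withdrawal counts or rates. With at most 60 subjects the actual number may be small or zero. The change is worth making because it is cheap and must be fixed before the data are seen. It does not undermine the trial's main analysis.

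**What to change.** Change the analysis definition only and leave the withdrawal rule as it is. In the Analysis paragraph:

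- Define the set as subjects with mean compliance of at least 90% over their time on study drug who either completed or were withdrawn for confirmed FPG ≥ 300 mg/dL. State what *completed* means, including for a subject first found above the limit at week 16.
- Count those withdrawn for FPG ≥ 300 mg/dL as not reaching HbA1c < 7.5%.
- For the HbA1c change, use their last on-treatment value, for example week 8. This keeps the planned repeated measures ANOVA and a result in HbA1c points. A worst-rank comparison would fit neither.
- Report their number by arm beside the result.

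The set should not be opened to all compliant non-completers, because those who left for other reasons would have no outcome rule.

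The cost is a few sentences of text and one line in a table. There are small downsides. Compliance is measured over a shorter period for these subjects. A week 8 value stands in for week 16 and may understate the failure. The set is no longer a pure completer set. Subjects withdrawn before week 8 may have neither a pill count nor an on-treatment HbA1c, and should be listed separately by arm.
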